# *In addition to the information provided in this protocol, the original research proposal will be included with the IRB application. The focus of this IRB application is on intervention participants.*

# Project Summary:

Chronic inflammation underpins the development of numerous chronic diseases that contribute significantly to disability and mortality in the United States (US). Of particular interest, as it relates to inflammation, is diet which is a strong moderator of systemic inflammation. Diets high in fruit and vegetable intake, fish, and whole grains (e.g., Mediterranean and vegetarian diets) have been associated with lower levels of inflammation. On the other hand, diets rich in red meat, high-fat dairy products, and refined grains (Western diet) are typically associated with higher levels of inflammation. Up until 2014, no dietary index has been designed specifically to determine the inflammatory potential of individual's diet. However, researchers in the Cancer Prevention and Control Program, University of South Carolina developed the Dietary Inflammatory Index™ (DII). The DII quantifies the level of dietary inflammatory potential on a scale from maximally anti- to pro-inflammatory. Watermelon is one of the fruits whose components have been shown to have anti-inflammatory effects. The overall objective of this proposal is to determine if a refined and modified watermelon-focused DII counselling system can reduce levels of chronic inflammation. The DII is a validated measure that has been shown to predict a range of outcomes including inflammation, cancer, CVD, and mortality, among others.

Specifically, the aims of this proposal are to:

- 1. Refine and modify the DII-based intervention by developing and incorporating numerous watermelon recipes which will score low (anti-inflammatory) on the DII scale.
- 2. Design and implement a two-arm intervention trial based on the refined watermelon-focused DII-based program for reducing levels of chronic inflammation. Each arm will have 15 participants (plus an additional 15 partners recruited by the intervention-arm participants). The intervention arm will receive the modified DII intervention whereas the control arm will receive general health education.

# **Target Population and Intervention Participants**

This non-randomized, two-arm trial will enroll and complete measurements on 30 individuals (n=30 control and n=30 intervention). Participants will be recruited from the broader Columbia, SC community, including African-American churches which we have worked with on several research studies conducted through the University of South Carolina to date. We will recruit participants from the community via fliers and listserv messages. The trial will be based at the main offices of the University of South Carolina's Cancer Prevention and Control Program in Columbia. Potential participants will be provided with a study information sheet which outlines inclusion and exclusion criteria (see below) and provides details about the study. If the individual is interested in participating, then they will complete a study contact sheet, which will be given to study staff at Connecting Health Innovations (CHI). Given we will be recruiting from African-American churches, as well as the general community, we expect to enroll mainly African Americans. However, recruitment will not be restricted on race or ethnicity.

Inclusion Criteria:

- Be ≥18 years of age
- Have no serious, unstable co-morbidity that would make participation in a diet and PA intervention difficult or risky
- Be willing and able to participate fully in the study for a period of three months
- Have Columbia, SC area residence and be able to travel to and from the clinic and intervention sites
- Have access to the Internet and a valid email address
- Not be currently enrolled in a weight loss study or actively taking weight loss medications.
- Have a body mass index (BMI, kg/m^2) between 25.0-49.9.

Exclusion Criteria:

- Serious, unstable co-morbidity that would make participation in a diet and physical activity intervention difficult or risky including renal disease retinopathy, peripheral vascular disease or neuropathy;
- Any medications that are known to influence CRP levels such as chronic steroid (e.g., prednisone) use;
- Diagnoses of congestive heart failure, chronic renal failure, chronic liver disease (including alcoholic cirrhosis), cancer within the past year (except for non-melanoma skin cancer);
- Actively receiving cancer treatment;
- Have had any major surgeries in the past 3 months;
- Poor performance status according to the World Health Organization definitions (i.e., Level 3: symptomatic, >50% in bed, capable of only limited self-care; or Level 4: bedbound); or
- Life expectancy <3 years, on hospice, nursing home or other institutionalized care.

Recent attention to behavioral interventions has pointed out limitations in traditional randomization schemes among these types of randomized controlled trials (e.g., inability to truly blind participants, lack of decision making by participants). Other methods of allocation, which take into account perceived ability to comply with intervention requirements, are much more appropriate for this kind of intervention. Therefore, we propose that only individuals who are motivated to make a healthy diet change will receive the intervention.

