Project staff will record the blood pressure of intervention participants using a standard blood pressure cuff after the participant has been resting for 5 minutes. Three readings will be taken with the second and third readings recorded. Staff also will measure body weight and height using an electronic scale and stadiometer, respectively. Hip and waist circumference will be measured using a Gulick™ measuring tape. Body composition will be obtained through BIA performed using the Tanita TBF-300WA Body Composition Analyzer (Arlington Heights, Illinois). Physical activity logs will be used to track participation in physical activity when the Actigraph is not worn. Participants height, weight, age, gender, smoking status, and handedness will be used to calibrate the Actigraph monitors. These monitors will be worn at all times and will only be taken off for bathing/showers or water activities. Participants will be provided the monitors for 7-10 days to ensure at least 4 days of complete data. Complete data will be at least 23 reported hours of armband wear time or wear time plus information provided in the physical activity logs (e.g., supplementing wear time with time spent swimming). Blood samples will be collected by trained phlebotomists for characterization of the biomarkers identified above. Online questionnaires will be provided to all participants to complete at each data collection point. Project staff will assist with completion as necessary. Questionnaires will include items to assess sociodemographic characteristics, health behaviors, social desirability and approval, self-reported physical activity, stress, depression, and confidence in the ability to make lifestyle changes. Self-report 24-hour dietary recalls will be provided with an online pass to our IMAGINE Healthy Online Portal to provide support and information in relationship to the weekly classes. Access to this material typically requires a fee. Therefore, the intervention participants will gain access through the study, but the controls will not be able to access this material. This limits the likelihood of "exposure contamination" by the controls.

Participants, but not their invited partners, will be provided with a \$20 incentive for baseline assessment measures and \$20 incentive the 3-month measures. Control participants will receive the same incentives.

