#### **Potential Risks**

Potential risks include the possibility that some questions included in the questionnaire may make some respondents feel uncomfortable (for example, inquiries about their diet, physical activity, smoking and alcohol habits). However, respondents may refuse to answer any question. The phlebotomy component carries a slight risk associated with venipuncture (redness, swelling, etc.). Phlebotomy will be undertaken by an experienced phlebotomist trained to minimize any risk associated with this portion of the study. All blood draws will take place at USC's CPCP by a trained phlebotomist. There is virtually no risk to the subjects from the lab assays, which are routinely used in clinical practice. Participants may experience discomfort, irritation, or in rare cases, a skin reaction to the Actigraph (worn for 7 days 3 times during the study). However, it is very similar to a wrist watch and any reactions would be rare. We will discuss ways to limit irritation and instruct participants about discontinuing use if an allergic reaction occurs. The BIA machine carries virtually no risk. It is essentially the same as standing on a typical weight scale. However, in between each participant, the scale will be cleaned as it requires the participant to be bare-footed. The intervention itself is very unlikely to cause any serious harms. From our experience, we recognize that a healthy diet intervention will only aid in improving the health of our participants. We will encourage physical activity and provide education on physical activities. However, most of the physical activity will be performed outside of the study environment. Our experience has been that most subjects in our intervention studies in Columbia, South Carolina are pleased to be able to participate in health research.

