#### **Statistical Analyses**

Sample characteristics were described by intervention condition using frequencies and means. Differences between groups at baseline were derived with Fisher's exact test for categorical covariates given the small sample sizes. For continuous covariates, t-tests or Wilcoxon rank sums test, depending on normality, were used. Differences in daily average watermelon consumption were tested using t-tests. Outcomes included CRP, HbA1c percent, glucose, BMI, body fat percent, and body weight. Given the small

sample size, it was not possible to conduct a confounder selection process. However, all models were adjusted for age. Using general linear models with repeated measurements with a compound symmetry covariance structure, least-square means of the outcomes by intervention status were obtained. Next, an interaction term was added to investigate the intervention-by-time effect. This process was conducted for each outcome.

The IMAGINE-Watermelon program was designed to lower dietary inflammatory potential as measured by the E-DII. In theory, the intervention arm should have lowered their E-DII score (i.e., become more antiinflammatory) and the control arm should have stayed roughly the same. Adherence to the intervention assignment was examined based on change in the E-DII score. A *post-hoc* analysis was designed to examine whether a change to a more anti-inflammatory dietary pattern led to a change in inflammation regardless of intervention status. Participants were dichotomized at the median based on the change in their E-DII score (i.e., became more anti-inflammatory) and those above the median became more pro-inflammatory. For this *post-hoc* linear regression analysis, the independent variable was the change in the E-DII scores analyzed as both continuous and dichotomized at the median. Multiple least square regression was then performed to obtain least square means of the dependent variables by E-DII change adjusted for age. Additionally, the change in E-DII score was examined as a continuous measure where beta coefficients for a one-unit change in the E-DII score were reported. A one-unit increase in the change in E-DII score indicates a worsening of the E-DII score.

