#### **Inclusion of Women and Minorities**

All subjects will be U.S. citizens who are suspected of suffering from diet-associated chronic, systemic inflammation. The condition under study, chronic systemic inflammation is rampant in the US population; however, it is somewhat more prevalent among African Americans than in European Americans. Because we are recruiting from African-American churches and the general community of South Carolina, we expect that at least 75% of our population will be African American. Chronic, systemic inflammation afflicts both sexes and dietary quality, and therefore associated DII, will be well represented in both of the sexes. Therefore, we will attempt to recruit women and men in equal numbers. Men and women will be recruited and followed using the same procedures; therefore we anticipate that women and men will be recruited in the same numbers.

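### The entry criteria screen out several influences on weight and CRP but not pregnancy or recent delivery, although weight, BMI and BIA body fat are outcomes in small arms adjusted only for age

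*Combined protocol and SAP*

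**What the plan says.** Under Target Population and Intervention Participants, the age criterion is a lower limit only, "Be ≥18 years of age", and BMI must lie between 25.0 and 49.9. The inclusion list bars concurrent weight-loss studies and weight-loss medication. The exclusion list covers medication known to influence CRP, major surgery in the past 3 months, active cancer treatment, and "Diagnoses of congestive heart failure, chronic renal failure, chronic liver disease (including alcoholic cirrhosis), cancer within the past year". A general clause excludes "Serious, unstable co-morbidity that would make participation in a diet and physical activity intervention difficult or risky". Pregnancy and recent delivery appear in neither list, nor anywhere else in the supplied text.

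Under Inclusion of Women and Minorities, the protocol states that "we will attempt to recruit women and men in equal numbers".

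Under Statistical Analyses, "Outcomes included CRP, HbA1c percent, glucose, BMI, body fat percent, and body weight". All models adjust for age and for no other covariate. Under Sources of Materials, measurements are taken at baseline and after week 12, and "Body composition will be obtained through BIA performed using the Tanita TBF-300WA Body Composition Analyzer".

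**The concern.** Several entry criteria exist to keep non-dietary influences away from the outcomes: CRP-active drugs, weight-loss drugs, other weight-loss programmes and recent surgery. Pregnancy and the months after delivery are influences of the same kind on weight, BMI and estimated body fat. They act over the same 12 weeks and do not depend on the intervention. Leaving them out is inconsistent with the protocol's own approach.

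Nothing later in the plan makes up for it. Age adjustment does not remove the effect of a pregnancy, and no rule says how to treat values affected by one that begins during follow-up. The post-hoc regressions on change in E-DII score draw on the same participants and would carry the same outlying values. With small arms, one person has visible weight in the arm mean and in the residual variance.

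**Working it through.** The plan gives no sample-size calculation, SD or effect size, so there is no figure of its own to reproduce. The check asks how far one affected participant moves the comparison of weight change.

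**Inputs from the protocol**
- Arm size: the Project Summary gives 15 per arm plus 15 partners on the intervention side, and Participation Expectations (Intervention) also describes a group of 15 plus partners. Target Population and Intervention Participants gives 30 control and 30 intervention, in a sentence that also says 30 individuals. Both n = 15 and n = 30 are used below.
- Time points: baseline and week 12.

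**Assumptions (not in the documents)**
- Extra weight change due to pregnancy over 12 weeks: x = 4 to 6 kg.
- SD of 12-week weight change: 3 kg, range 2 to 5 kg.

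**Step 1. Shift in the arm mean, x/n**
- n = 15: 4/15 = 0.27 kg; 6/15 = 0.40 kg.
- n = 30: 4/30 = 0.13 kg; 6/30 = 0.20 kg.

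**Step 2. SE of the difference in mean change, SD × √(2/n)**
- n = 15: 0.73 kg for SD 2; 1.10 kg for SD 3; 1.83 kg for SD 5.
- n = 30: 0.52, 0.77 and 1.29 kg.

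**Step 3. Shift in SE units**

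| n | SD 2 kg | SD 3 kg | SD 5 kg |
|---|---|---|---|
| 15 | 0.37-0.55 | 0.24-0.37 | 0.15-0.22 |
| 30 | 0.26-0.39 | 0.17-0.26 | 0.10-0.15 |

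**Step 4. Spread in the affected arm, √(SD² + x²/n)**
- With SD 3, n = 15 and x = 5 (the middle of the range): √(9 + 25/15) = 3.27 kg, against 3.0 kg without the affected participant.

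**Step 5. Which outcomes this covers**
- BMI is weight divided by squared height, and adult height is essentially fixed. It therefore moves with weight and is not independent evidence.
- BIA body fat is also exposed, but the documents give nothing from which to size the effect.
- No figure is available for CRP, HbA1c or glucose, so none is claimed.

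**Step 6. Do other criteria close the gap?**
- The general co-morbidity clause does not clearly reach a healthy pregnancy.
- The surgery criterion might catch some surgical deliveries within 3 months, but not a current pregnancy or other deliveries.

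**The case against.** The case against giving this much weight has several parts.

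- **Low probability.** The chance of such an enrolment depends on an age mix that the documents do not give. This stands.
- **No clear direction.** A pregnancy could fall in either arm, and nothing suggests one arm over the other. Before the event, the effect is mainly added noise. If it happens, however, the realised comparison is displaced in one direction.
- **Unseen safeguards.** The phone screener's content is not shown, consent pages are not in the supplied text, and the protocol's opening note says that the original research proposal accompanies the application. A pregnancy question may sit in one of these. This also stands. The finding is that the stated criteria give no ground for excluding a pregnant applicant, not that no one will ask.
- **Timing.** Statistical Analyses is written in the past tense, so a change to the screener may come too late. That changes the remedy, not the finding.

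Two stronger readings do not hold. A reader might infer that one such participant distorts most of the six outcomes. Only weight has been sized, BMI follows from it, and nothing in the documents quantifies an effect on the blood markers. A reader might also note that people with implanted electronic devices are not excluded and conclude that BIA is given without a needed safety screen. Potential Risks says "The BIA machine carries virtually no risk. It is essentially the same as standing on a typical weight scale", and no other section contradicts it. The hazard would rest on outside knowledge alone, so it forms no part of this point. Nor is there any documented route from a device to weight, BMI, CRP, HbA1c or glucose.

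**Conclusion.** The gap is real and limited. As written, the criteria admit women who are pregnant or recently delivered, and the analysis has no means of handling their data. Under the stated assumptions, one pregnant participant shifts the arm's mean weight change by 0.27-0.40 kg at n = 15, roughly 0.15-0.55 SE of the arm difference, or by 0.13-0.20 kg at n = 30. Even the upper end is well below one standard error, so a single case is unlikely to decide the result alone. It is avoidable error in a small trial, with low probability and moderate size. The conclusion rests on the assumed 4-6 kg and the assumed SD of 2-5 kg. It also depends on which arm size is correct, which the protocol must settle.

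**What to change.** 1. Add to the exclusion criteria: pregnant, planning pregnancy during the study, or recently post-partum, with the post-partum interval defined.
2. Ask about this on the existing phone screener, and ask about pregnancy again at week 12.
3. Report a sensitivity analysis that omits the values of anyone who reports a pregnancy. Keep this as a sensitivity analysis: removing those values from the main comparison would be a post-baseline exclusion in a small non-randomised trial, which is itself debatable.
4. If enrolment is already complete, report whether any participant was pregnant or recently post-partum and run the same sensitivity analysis.
5. Reconcile the two statements of arm size.

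The cost is a self-report question at two time points, a few lines of protocol text, one additional analysis, and the loss of a few otherwise eligible recruits.

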#### **Recruitment and Consent Procedures**

Fliers will be distributed at a couple of African-American churches which have participated in previous Cancer Prevention and Control Program (CPCP) studies, as well as general community locations, including but not limited to USC. Additionally, recruitment efforts will utilize target listserv messages. Once a potential participant is identified, he or she will be provided with a study information sheet which outlines inclusion and exclusion criteria (see below) and provides details about the study. If the patient is interested in participating, then they will complete a study contact sheet, which will be given to researchers at CHI. After an individual has been identified and completed a contact form, CHI staff will contact the patient and conduct a brief phone screener with them. If the individual qualifies, they will be asked to schedule a group orientation meeting time that is convenient for them. Numerous studies, including those conducted by this study's staff, have indicated greater commitment and motivation to participate in health behavior interventions when undergoing that intervention with a family member or close friend. Therefore, intervention participants will be asked to invite one person to the intervention classes.

At this group orientation, participants will learn more about the study and what will be involved. They will be given consent forms to complete. Once consented, they will be instructed on completing the baseline questionnaires and the 24-hour Dietary Recall (ASA24TM). Participants also will be instructed on using the Actigraph GT3X-BT for 7 days (more detail is under Participant Expectations) to measure physical activity and sleep. After this meeting, participants will have two weeks before the start of the study. During that time, they will complete the 7 days of wearing the Actigraph and will complete four days of dietary reporting using the 24-hour Dietary Recall (ASA24TM). In addition, the participant will visit the CPCP where they will have their height and blood pressure assessed, and laboratory blood work done (more detail is under Participant Expectations). Once visits are completed and at least 7 days have passed, the study coordinator will collect the Actigraph from the participants. Participants selected as controls will complete all of the same measures the primary participants will do but will not receive the intervention and will not need to attend the orientation session.

After all baseline measures are completed, participants will start the weekly group sessions. After at least one class has been completed, the study nutritionist will provide participants with an individualized counseling session to provide individualized guidance on study-related dietary and exercise requirements.

#### **Participation Expectations (Intervention)**

One groups of 15 individuals, plus their invited partners, will meet weekly for 12 weeks to cook, and engage in exercise and stress-reduction activities. This 3-month intervention will involve participants' convening weekly for 12 consecutive weeks. Participants will be expected to attend baseline and post-intervention (i.e., 12-weeks) clinic sessions. Intervention classes will meet on the same night at the same time for each of the weekly classes. Participants will have access to online material through our IMAGINE Healthy Online Portal

